Between 7 to 14 days after the last study visit, participants will return to the study site for a safety follow-up visit. The procedures to be completed during the follow-up visit are listed in the SoA.

NUMBER OF PARTICIPANTS

Approximately 164 participants will be enrolled in this study.

INTERVENTION GROUPS AND DURATION

Study intervention will be taken at home in the morning (C mg JNJ-55308942 or placebo) at approximately the same time (\pm 4 hours) each day 30 minutes after the start of breakfast (maximum of 2 hours after the start of breakfast). There is an exception on Day 1 where participants will receive the study intervention at the study site after all baseline assessments have been completed. On study visits 3, 4, 5 and 6, study intervention will be taken at the study site after the clinical lab and PK samples have been collected and at approximately the same time (\pm 4 hours). Study intervention will be dispensed at visits 2, 4 and 5 during this double-blind treatment period. When the participant returns to the site for visit 3, 4, 5 and 6, the participant will be administered the study intervention from the bottle dispensed from the previous visit.

The capsules must be swallowed whole and not chewed, divided, dissolved, or crushed.

The first dose of study intervention will be taken in the fed condition on Day 1 of the double-blind treatment phase when the participant is at the study site.

On days when participants visit the study site, they should not take the study intervention at home before arriving at the site. The participants will bring the study intervention with them at each study visit and will take study intervention—from the bottle dispensed at the previous study visit—at the site in the fed condition after completion of predose study assessments and blood collections. Dosing at the study site will be witnessed by the study staff.

Description of Interventions

Group/Arm Name	Active study intervention group	Placebo group
Intervention name:	JNJ-55308942	Placebo for JNJ-55308942
Dosage formulation	Capsule	Capsule
Unit dose strength(s)/ Dosage levels:	C mg	Not applicable
Dosage Level(s) and Frequency	C mg, 1 capsule once-daily	1 capsule once-daily

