Placebo-control reminder script (PCRS)		X ^l	X	X		X		X	
Structured Interview Guide for MADRS (SIGMA)		X ^l	X	X		X		X	
CGI-S		X ^l	X	X		X		X	
Participant Self-Rating Assessments									
SHAPS		X ^l						X	
PROMIS-Ability to Participate in Social Roles and Activities		X ^l	X	X	X	X	X	X	
PHQ-9		X ^l	X	X	X	X	X	X	
GAD-7		X ^l		X		X		X	
SAWB ^o			X-----X						
Ongoing Participant Review									
Concomitant therapy									Continuous
Adverse events									Continuous

Footnotes:

- a) The procedures scheduled during the screening visit may be divided over multiple days, according to operational and/or site/country-specific needs. A \pm 1 day window will be allowed for study days 8, 15, 22, 29, 36 and 43.
- b) Must be signed before first study-related activity.
- c) The use of the digital health assessment app is mandatory.
- d) Performed for women of childbearing potential (WOCBP). Serum (β -hCG) pregnancy test performed at Screening. At all other time points, urine pregnancy test will be done. If positive, a serum β -hCG test will be performed. Investigators may perform additional pregnancy testing at their discretion as clinically needed.
- e) 12-lead ECG and vital signs will be taken predose of study intervention.
- f) There are 2 versions of the C-SSRS. A “baseline/screening” version will be conducted at screening. A “since your last visit” version will be conducted predose on visit 2, 3, 4, 5, and 6, at follow-up/early withdrawal.
- g) 12-lead ECG should be performed in triplicate at screening.
- h) If a participant discontinues study intervention before the end of the double-blind phase, early withdrawal (EW) visit should be completed.
- i) Study intervention will be taken at home in the morning at approximately the same time (\pm 4 hours) each day, 30 minutes after the start of breakfast (maximum of 2 hours after the start of breakfast). Recommended to take each dose of study intervention with a glass of water.
- j) On study visits 3, 4, 5, and 6, study intervention will be administered at the study site. The participants are instructed to eat at home and come to the site within an hour or less after completion of the meal. Inability to comply with these instructions would not constitute a protocol violation but the patients are encouraged to comply with these instructions. Dosing should be witnessed by the study staff when study intervention is taken at the study site.

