Study 55308942EDI1003 was an open-label drug interaction study in healthy male and female participants to evaluate the effects of multiple doses of JNJ-55308942 on CYP3A4, CYP2D6, and CYP2C19 activity.

Human Pharmacokinetics and Product Metabolism

Following single oral doses of JNJ-55308942 solution in study 55308942EDI1001 CCI to CCI mg) under fasted conditions, the T_{max} was within CCI to CCI hours and the half-life ($T_{1/2}$) ranged from C to CC hours across doses.

Mean exposure parameters (C_{max} , AUC_{0-24h} , AUC from time zero to the time of the last quantifiable concentration [AUC_{last}], and AUC from time zero to infinite time [AUC_{∞}]) increased generally in a dose proportional manner.

After a single dose administration of C mg JNJ-55308942 in the presence of food, C_{max} and AUC_{∞} were decreased by 28% and 18%, respectively, compared to when dosed in the fasted state.

After once-daily dosing with C to C mg JNJ-55308942 for 10 consecutive days in healthy male and female participants, the mean $T_{1/2}$ values after steady-state administration were similar to the mean $T_{1/2}$ values after a single dose, suggesting no time-dependent mechanisms are involved in the metabolism of JNJ-55308942. The average Day 10 to Day 1 accumulation ratio ranged between 1.98 and 2.51 after once-daily dosing. Mean $T_{1/2}$ values at steady-state were similar among the different doses.

At C mg once-daily for 10 days, JNJ-55308942 was the major circulating entity in plasma. Major metabolites M9 and M5 (hydrolysis of 5-fluoropyrimidine- triazole bond and subsequent

glucuronidation) were estimated as 5.9% and 4.2% of unchanged drug and were deemed as the most important metabolites, but none of the metabolites reached 10% of JNJ-55308942 concentrations.

A drug-drug interaction study (55308942EDI1003) showed that JNJ-55308942, at steady-state after once-daily administration of **CC** mg dose (solution), is a weak inducer of CYP**CCI** and a moderate inhibitor of CYP**CCI**. There was no clinically significant inhibition observed for CYP**CCI**.

Efficacy/Safety Studies

JNJ-55308942 was generally safe and well tolerated. Overall, there were no safety concerns observed in healthy adult participants after the repeated dosing of JNJ-55308942 either alone or in combination with a drug cocktail consisting of **CCI**

There were no deaths, SAEs, or treatment emergent adverse events (TEAEs) leading to discontinuation during any of the studies.

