8.1.4. Follow-up or Early Withdrawal Visit (Visit 7)

All participants will have to complete Visit 7 (final follow-up visit or early withdrawal visit). Participants who prematurely withdraw from the study are encouraged to complete Visit 7. During Visit 7, all assessments will be completed per the SoA.

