Participants who are enrolled in the study will continue on their current medication regimen, if applicable, throughout the study. No dose changes are permitted from screening through the end of the study (until after the follow-up visit). No concurrent use of antidepressants will be allowed until after the follow-up visit.

For each participant, the study will consist of 3 phases: a screening phase of up to 4 weeks, a double-blind treatment phase of 6 weeks, and a post-treatment follow-up phase of up to 2 weeks (Figure 1). After giving written informed consent for screening, participants will be screened between 28 days and 1 day before the double-blind treatment phase to ascertain their eligibility for the study according to the inclusion and exclusion criteria. Eligible participants will enter the double-blind treatment phase where they will be randomly assigned with a 1:1 ratio to once daily administration with mg JNJ-55308942 or placebo for 6 weeks, Day 1 up to and including the last treatment visit, Day 43 +/- 1 day. Between approximately 1 to 2 weeks after administration of the last dose, participants will return to the study site for a follow-up visit. The total study duration for each participant will be up to 12 weeks. There will be 7 scheduled visits to the study site during the study, including screening and follow-up visit.

Treatment Period Follow-up Visit Screening (Efficacy/Safety) **Study complete** Up to 4 weeks Double-blind, 6 weeks BD type I and II in a current MDE All participants 1-2 weeks **Include GoF P2X7 mutation** Placebo Exclude complete LoF P2X7 mutations JNJ-55308942 Up to 4 weeks 6 weeks At 6 weeks: **Primary endpoint MADRS**

Figure 1: Schematic Overview of the Study

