5.1.1. Analysis Phases

Screening

The screening phase begins on the date the first informed consent is obtained and ends 1 day before the first dose of study intervention in the double-blind treatment phase. The screening phase end date is left missing for those participants who did not receive study intervention.

Double-Blind Analysis Phase

The analysis reference start date of the double-blind analysis phase is the date of the first dose of the double-blind study intervention. The analysis reference end date of the double-blind analysis phase is the date of study disposition (last contact).

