	Double-Blind	2	Baseline	≤1	1
		3	Week 1	[2,11]	8

CONFIDENTIAL – FOIA Exemptions Apply in U.S.

12

Table 2: Visit Windows

Parameter	Analysis Phase	Scheduled Visit Number	Time Interval (Label on Output)	Time Interval (Day)*	Target Time Point (Day)*
		4	Week 2	[12,21]	15
		5	Week 4	[22,35]	29
		6	Week 6	≥36	43

^{*}Relative to Study Day 1; FU/EW = Follow-up/Early Withdrawal

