5.6.3. Additional Safety Assessments

5.6.3.1. Clinical Laboratory Tests

Descriptive statistics of chemistry, hematology, and urinalysis (pH and specific gravity) laboratory tests and changes from baseline will be presented at each scheduled time point by intervention group.

Abnormality criteria based on normal ranges will be applied to baseline and postbaseline values. Shift tables will be provided summarizing the shift in laboratory values from baseline to scheduled time points with respect to abnormality criteria (low, normal, high). A listing of participants with any laboratory results outside of the reference ranges will be provided.

A listing of participants meeting any of the following hepatic toxicity stopping criteria (confirmed by repeat testing) will be provided:

• Aspartate aminotransferase (AST) exceeds 5x the upper limit of normal (ULN)

- Alanine aminotransferase (ALT) exceeds 5x the ULN
- AST exceeds 3x the ULN and total bilirubin exceeds 1.5x ULN
- ALT exceeds 3x the ULN and total bilirubin exceeds 1.5x ULN

The number and percentage of participants with positive urine drug screen results will be presented over time by intervention group.

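### SAP Table 2 puts early-withdrawal visits and completers' post-treatment follow-up in one analysis visit, which dilutes early-withdrawal findings in by-visit safety tables that have no worst on-treatment counterpart

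*SAP*

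**What the plan says.** SAP Section 5.1.2, Table 2, has one Visit 7 category for laboratory tests, vital signs, 12-lead ECG, C-SSRS, urine drug screen, physical examination and body weight. Its footnote reads "FU/EW = Follow-up/Early Withdrawal". The target is Day 49 to 56, and the supplied text shows no day interval for the row. The Week 6 safety window closes just before the day of that visit.

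The protocol uses the visit for two purposes:

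- Section 8.1.4: "All participants will have to complete Visit 7 (final follow-up visit or early withdrawal visit".
- Schedule of Activities, footnote h: "If a participant discontinues study intervention before the end of the double-blind phase, early withdrawal (EW) visit should be completed".
- Synopsis, for completers: "Between 7 to 14 days after the last study visit, participants will return to the study site for a safety follow-up visit". SAP Section 1.2 agrees: "Between approximately 1 to 2 weeks after administration of the last dose, participants will return to the study site for a follow-up visit".

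SAP Section 5.1.1 runs the double-blind analysis phase to last contact, so no analysis phase separates on-treatment from post-treatment values.

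Section 5.6.3.1 plans the laboratory summaries by visit: "Shift tables will be provided summarizing the shift in laboratory values from baseline to scheduled time points with respect to abnormality criteria". Sections 5.6.3.2 and 5.6.3.3 likewise tabulate vital-sign abnormalities (including weight) and non-QTc ECG abnormalities by time point. Section 5.6.3.2 limits the vital-sign incidence to the intervention period but does not say which visits that covers.

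**The concern.** A row that combines recently treated participants with participants one to two weeks past their last dose does not answer either safety question. It does not describe what is seen around the time of stopping, and it does not describe recovery after treatment. The two groups also differ by selection: one consists of people who stopped early, and the discontinuation reasons in Protocol Section 7.2 include tolerability and liver enzymes.

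The EW visit can matter for an individual. On-treatment laboratory tests after baseline are scheduled only at Days 15, 29 and 43, so for someone who stops before Day 15 the EW sample may be the only scheduled post-baseline laboratory result. Safety and tolerability is a stated secondary objective (SAP Section 1.1). What is at stake is how readable the between-arm descriptive comparison is. No hypothesis test is involved.

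**Working it through.** **1. Plan's own figures.** Inputs from SAP Section 3: effect size 0.45, 1-sided alpha 0.10, power 90%, dropout 20%.

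- n per arm = 2 × (1.2816 + 1.2816)² / 0.45² = 64.9, so 65.
- 65 / 0.8 = 81.25, so 82 per arm and 164 in total, as stated.
- The plan expects 132 completers, which leaves 164 − 132 = 32 early withdrawals, or 16 per arm beside 66 completers.

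**2. Share of the row that is EW.** This assumes one Visit 7 record per participant and full attendance by completers.

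- All who withdraw attend: 16 / 82 = 19.5%.
- Three quarters attend: 12 / 78 = 15.4%.
- Half attend: 8 / 74 = 10.8%.

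**3. Are completers off drug at follow-up?** Protocol Section 2.2 states: "The average Day 10 to Day 1 accumulation ratio ranged between 1.98 and 2.51 after once-daily dosing". The half-life itself is redacted. If one-compartment kinetics are assumed, the accumulation ratio is R = 1 / (1 − e^(−24k)), so the fraction remaining after 7 days is (1 − 1/R)^7.

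- R = 1.98: 0.495^7 = 0.7% (half-life about 24 h).
- R = 2.51: 0.602^7 = 2.9% (half-life about 33 h).

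On that assumption the follow-up visit is close to drug-free. No similar statement is possible for EW, because the documents set no interval between last dose and EW visit.

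**4. Dilution.** Let p be the abnormality rate at EW and q the rate at follow-up. The pooled rate is (16p + 66q) / 82. The documents give neither rate, so a range is shown:

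| | p = 10% | p = 20% | p = 30% | p = 50% |
|---|---|---|---|---|
| q = 0 | 2.0% | 3.9% | 5.9% | 9.8% |
| q = 2% | 3.6% | 5.5% | 7.5% | 11.4% |
| q = 5% | 6.0% | 7.9% | 9.9% | 13.8% |

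With clean follow-up the dilution is 82 / 16 = 5.1-fold. With q of 2% to 5% it is 1.7- to 4.4-fold. If only half attend and follow-up is clean, the ratio rises to 74 / 8 = 9.3-fold, but half as many EW values are then involved.

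**5. Effect on an arm comparison.** Take illustrative EW rates of 30% and 10%, with q = 2% in both arms. The pooled rates are (4.8 + 1.32) / 82 = 7.5% and (1.6 + 1.32) / 82 = 3.6%. A 20-point difference at EW shows as 3.9 points.

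**6. Which assignment rule applies.** The Week 6 windows, and the single post-baseline weight and physical-examination window, are cut at the FU/EW day, which suggests assignment by label. The Week 1, 2 and 4 windows for the other parameters have no such cut, and the general rule assigns visits by study day. Suppose a participant attends on Day 15 and has an EW visit on Day 20. Both fall in the Week 2 window [12,21] with target Day 15. The closest-to-target rule keeps Day 15 (distance 0) and leaves Day 20 (distance 5) out of the summaries. One reading dilutes the EW value, and the other can drop it from the by-visit tables.

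**The case against.** The strongest reply is that little is lost, because many outputs do not depend on the label:

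- TEAEs are counted through 30 days after the last dose, and those leading to discontinuation are tabulated separately.
- QTc increases and shifts use the maximum postbaseline value, and C-SSRS shifts use the maximum postbaseline score.
- Out-of-range laboratory results, confirmed hepatic stopping criteria, abnormal vital signs and relevant ECG findings are listed.
- YMRS has no Visit 7 row.

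All of this stands. It rules out the inference that the safety tables hide these abnormalities. What remains is that a listing is not a between-arm summary, and that laboratory tests, vital signs, weight and non-QTc ECG parameters have no maximum or worst-value table.

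A reader might also infer that the Week 1 to 6 rows lose the values that prompted withdrawal, so that on-treatment safety looks better than it was. The documents do not support this. The EW visit follows the decision to stop, and values from earlier scheduled visits stay in their weekly rows. The liver criteria need repeat confirmation before they are met. An on-treatment mean shift is still estimated in the weekly rows, and the dilution applies to the FU/EW row only.

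Nor can EW values be taken as on-drug. No interval from last dose is set, the Schedule of Activities heads the shared column with the 7-to-14-day interval, and withdrawn participants are only encouraged to attend. This limits the size of the effect, but it is also a reason to classify values by time since last dose.

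Finally, moving EW values into the weekly windows could backfire, because the closest-to-target rule could then discard them. That objection is correct and shapes the fix.

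**Conclusion.** The concern holds as a matter of dilution and ambiguity in descriptive by-visit tables. One analysis visit mixes EW and post-treatment follow-up. For laboratory tests, vital signs (including weight) and non-QTc ECG parameters, no planned summary recovers the on-treatment picture across all visits. At the planned dropout with full attendance, EW is about 20% of the row, and an EW abnormality rate is shrunk about 5-fold if follow-up is clean, or 1.7- to 4.4-fold with an assumed 2% to 5% background. These sizes rest on assumed abnormality rates, assumed attendance, and EW visits occurring close enough to the last dose to differ from follow-up.

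The documents do not show that abnormalities are concealed or that the weekly rows are biased. The primary analysis is not affected. The change is worth making because it is inexpensive and makes the safety comparison interpretable.

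**What to change.** - In SAP Table 2, replace the combined category with two rows, Early Withdrawal and Follow-up, for every parameter that now uses it.
- State in Section 5.1.2 that EW visits are assigned by visit label, whatever the study day, and do not compete for a weekly window. Do not move EW values into the weekly windows.
- Add a worst on-treatment summary by arm for laboratory tests, vital signs (including weight) and ECG. It should use scheduled, unscheduled and EW values within a prespecified interval of the last dose. Fix that interval before unblinding and justify it from the half-life known to the sponsor.
- Use the same interval to define which vital-sign values count as occurring during intervention in Section 5.6.3.2.

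The cost is SAP wording, one programming rule and a few extra tables. No new data, visits or participants are needed.

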5.1.3. Imputation of Efficacy

Imputation for missing data will include the following methods (Table 3).

Table 3: Imputation of Missing Efficacy Data

Imputation	Text
Multiple Imputation (MI)	1) Copy Reference
method	2) Delta Adjustment.
Non-Responder	Participants with missing values will be imputed as non-responders.
Non-Remitter	Participants with missing values will be imputed as non-remitters.

Imputation of total scores will apply only to the MADRS. Imputation of the MADRS total score will be performed only when 1 item score is missing. If 2 or more items are missing, the total score will be left missing. The total score will be imputed by calculating the sum of the scores of the non-missing items and multiplying it by the ratio of the maximum possible number of items (i.e., 10) to the number of non-missing items (i.e., 9).

For all other efficacy scales where multiple items are summed to create a total score, if any item of the scale is missing on one visit, the total score for that scale at that visit will be left missing.

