On study visits 3, 4, 5, and 6, study intervention will be administered at the study site after the clinical lab and PK samples have been collected and at approximately the same time (\pm 4 hours). Study intervention will be dispensed at visits 2, 4, and 5 during this double-blind treatment period. When the participant returns to the site for visit 3, 4, 5 and 6, the participant will be administered the study intervention from the bottle dispensed from the previous visit.

Of note, on study site visits 3, 4, 5, and 6, participants will be instructed to eat breakfast at home and come to the site within 1 hour or less after completion of the meal. Inability to comply with these instructions would not constitute a protocol violation, but the participants are encouraged to comply with these instructions as closely as possible.

The well-being of the participant will be frequently tracked using a Digital Health Assessment app to monitor parameters such as, but not limited to, the pattern of sleep, energy level, and concentration level via the SAWB Questionnaire. Additionally, the Digital Health Assessment app will alert the investigator when a participant has indicated that their depression is 'much worse' or 'very much worse' when answering weekly questions on depression.

The SHAPS will be administered once at baseline (pre-dose) and once at the end of the double-blind treatment phase (after the final dose). Participants will complete the PROMIS - Ability to Participate in Social Roles and Activities and the PHQ-9 at baseline and once weekly, and the GAD-7 every two weeks. As per SoA, the self-rating instruments will be administered at clinic visits or at home. For self-rating instruments completed at home on paper, participants should complete these scales before the next clinic visit and participants will receive notifications from the Digital Health Assessment app on their mobile phones as reminders to complete these paper instruments.

Key safety assessments will include the monitoring of adverse events, physical examinations, vital signs (e.g., blood pressure, pulse/heart rate, body temperature), electrocardiogram (ECG), clinical laboratory tests, emergence of mania (YMRS), and suicidal ideation (C-SSRS).

In addition, blood samples for PK, biomarker assessment, hormones (males only), and pharmacogenomics (general SNPs and RNA) will be collected as per the SoA and use of concomitant medication will be recorded.

Follow-up Examination

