these instructions would not constitute a protocol violation, but the participants are encouraged to comply with these instructions as closely as possible.

The well being of the participant will be frequently tracked using a Digital Health Assessment app to monitor parameters such as, but not limited to, the pattern of sleep, energy level, and concentration level via the SAWB Questionnaire. Additionally, the Digital Health Assessment app will alert the investigator when a participant has indicated that their depression is ‘much worse’ or ‘very much worse’ when answering weekly questions on depression.

The SHAPS will be administered once at baseline (pre-dose) and once at the end of the double-blind treatment phase (after the final dose). Participants will complete the PROMIS – Ability to Participate in Social Roles and Activities and the PHQ-9 at baseline and once weekly, and the GAD-7 every two weeks. As per SoA, the self-rating instruments will be administered at clinic visits or at home. For self-rating instruments completed at home on paper, participants should complete these scales before the next clinic visit and participants will receive notifications from the Digital Health Assessment app on their mobile phones as reminders to complete these paper instruments.

Key safety assessments will include the monitoring of adverse events, physical examinations, vital signs (e.g., blood pressure, pulse/heart rate, body temperature), electrocardiogram (ECG), clinical laboratory tests, emerging of mania (YMRS), and suicidal ideation (C-SSRS).

In addition, blood samples for PK, biomarker assessment, hormones (males only), and pharmacogenomics (general SNPs and ribonucleic acid [RNA]) will be collected as per the SoA and use of concomitant medication will be recorded.

Follow-up Examination

Between 7 to 14 days after the last study visit, participants will return to the study site for a safety follow-up visit. The procedures to be completed during the follow-up visit are listed in the SoA.

A diagram of the study design is provided in Section 1.2, Schema.

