5.1.2. Visit Windows

As participants do not always adhere to the protocol visit schedule, the following rules are applied to assign actual visits to analysis visits. Listed below are the visit windows and the target days for each visit. The reference day is Study Day 1 (which is the first day the study drug was taken in the double-blind treatment phase). If a subject has 2 or more actual visits in one visit window, the visit closest to the target day will be used as the protocol visit for that visit window. The other additional

visit(s) will not be used in the summaries or analyses. If 2 actual visits are equidistant from the target day within a visit window, the later visit is used.

All assignments will be made in chronological order. Once a visit date is assigned to a visit window, it will no longer be used for a later time point except for the endpoint. Listed below (Table 2) are the analysis visit windows and the target days for each visit defined in the protocol.

The baseline is defined as the last observation before the start of the first study intervention administration in the double-blind treatment phase. Assessments prior to Day 1 of the double-blind treatment phase that are not considered baseline assessments will be labeled as 'Screening'.

Table 2: Visit Windows

			Time Interval		
	Analysis	Scheduled	(Label on	Time Interval	Target Time
Parameter	Phase	Visit Number	Output)	(Day)*	Point (Day)*
MADRS,	Double-Blind	2	Baseline	≤1	1
CGI-S		3	Week 1	[2,11]	8
		4	Week 2	[12,21]	15
		5	Week 4	[22,35]	29
		6	Week 6	≥36	43
SHAPS	Double-Blind	2	Baseline	≤1	1
		6	Week 6	≥2	43
PROMIS, PHQ-9	Double-Blind	2	Baseline	≤1	1
, ,		3	Week 1	[2,11]	8
		4	Week 2	[12,18]	15
			Week 3	[19,25]	22
		5	Week 4	[26,32]	29
			Week 5	[33,39]	36
		6	Week 6	≥40	43
GAD-7	Double-Blind	2	Baseline	≤1	1
		4	Week 2	[2,21]	15
		5	Week 4	[22,35]	29
		6	Week 6	≥36	43
Clinical	Screening	1	Screening	<1	<1
Laboratory tests	Double-Blind	2	Baseline	≤1	1
(Hematology,		4	Week 2	[2,21]	15
Serum, Urinalysis)		5	Week 4	[22,35]	29
		6	Week 6	[36, Day of FU/EW)	43
		7	FU/EW		49 to 56
Vital signs,	Screening	1	Screening	<1	<1
12-lead ECG,	Double-Blind	2	Baseline	≤1	1
C-SSRS,		3	Week 1	[2,11]	8
Urine Drug Screen		4	Week 2	[12,21]	15
		5	Week 4	[22,35]	29
		6	Week 6	[36, Day of FU/EW)	43
		7	FU/EW		49 to 56
Physical	Screening	1	Screening	<1	<1
examination,	Double-Blind	2	Baseline	≤1	1
Body weight		6	Week 6	[2, Day of FU/EW)	43
		7	FU/EW		49 to 56
YMRS	Screening	1	Screening	<1	<1

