5.4.1. Secondary Endpoints of Special Interest

5.4.1.1. Snaith-Hamilton Pleasure Scale (SHAPS)

5.4.1.1.1. Definition

The SHAPS is a reliable, valid, and unidimensional instrument to assess hedonic capacity in adults with Major Depressive Disorder in the last few days. It is a 14-item, self-report tool with a completion time below 5 minutes. Each of the items has a set of 4 response categories: 1=Definitely Agree/Strongly Agree, 2=Agree, 3=Disagree, and 4=Strongly Disagree. The SHAPS total score is the sum of the 14 item scores, ranging from 14 to 56. A higher SHAPS total score indicates higher levels of current anhedonia (Nakonezny 2010).

Negative changes in the SHAPS total score indicate improvement.

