5.4.1.1.2. Analysis Methods

Descriptive statistics of the actual values at Baseline, Week 6, and the change from baseline to Week 6 will be presented for SHAPS total score by intervention group.

An analysis of covariance (ANCOVA) model will be used to test the difference of change from baseline at Week 6 in SHAPS total score between JNJ-55308942 mg once daily and placebo. The model will include intervention (placebo or JNJ-55308942), BD type (I or II), country, P2RX7 GoF SNP mutation genotype (homozygous or heterozygous), and concomitant medication status (no mood stabilizer or antipsychotic, a mood stabilizer alone, an antipsychotic alone, or a combination of a mood stabilizer and an antipsychotic) as factors, and baseline SHAPS total score as a covariate. Comparison between JNJ-55308942 mg once daily and placebo will be performed using appropriate contrast. Difference of least square means and 2-sided 80% CI will

be presented. Least square means of change from baseline (+/- SE) to Week 6 will be presented graphically.

Frequency distributions of the SHAPS individual items will be provided at each assessment time point.

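### One blank item voids a self-rated total, and a blank on the Day 1 form drops the participant from that scale's model, while the same gap on the MADRS is pro-rated

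*SAP*

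**What the plan says.** SAP 5.1.3 sets two rules for incomplete forms. For the primary scale, "Imputation of the MADRS total score will be performed only when 1 item score is missing": the sum of the nine answered items is multiplied by 10/9, and with two or more items missing the total stays missing. Beyond that, "Imputation of total scores will apply only to the MADRS". For any other efficacy scale built from summed items, "if any item of the scale is missing on one visit, the total score for that scale at that visit will be left missing".

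The scales under the second rule are SHAPS (14 items), PHQ-9 (9), GAD-7 (7) and the PROMIS short form (4). For SHAPS, SAP 5.4.1.1.1 states that "The SHAPS total score is the sum of the 14 item scores, ranging from 14 to 56". The ANCOVA in 5.4.1.1.2 takes change from baseline at Week 6 as the outcome, "and baseline SHAPS total score as a covariate". SAP 5.4.2.2.2, 5.4.2.3.2 and 5.4.2.4.2 use the primary MMRM for PROMIS, PHQ-9 and GAD-7, replacing baseline MADRS with the scale's own baseline.

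On baseline, SAP 5.1.2 says: "The baseline is defined as the last observation before the start of the first study intervention administration in the double-blind treatment phase". Protocol 1.1 says: "The SHAPS will be administered once at baseline (pre-dose) and once at the end of the double-blind treatment phase". The Schedule of Activities (Protocol 1.3) first collects all four scales on Day 1.

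**The concern.** The same gap, one unanswered item, is handled in opposite ways. On the MADRS it costs nothing. On a Day 1 self-rated form it leaves no baseline total, so both the change score and the covariate are undefined and every later record for that participant drops out of that scale's model. That is six post-baseline assessments for PHQ-9 and PROMIS, three for GAD-7 and one for SHAPS. The SAP does not say this in words, but it follows from its rules.

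Nothing else in the SAP recovers these participants. The multiple imputation in 5.3.2.1.2 is described only for the primary MADRS analysis. Appendix 2 (6.2) accepts Day 1 forms completed after the dose as baseline but gives no rule for an incomplete form. The version history explains that acceptance by a wish to use all the data collected, and the one-blank rule runs against that aim.

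At stake is precision on secondary endpoints. SHAPS, the first-listed secondary endpoint of special interest, is the most exposed: it has the most items, one baseline form and one post-baseline form.

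**Working it through.** **The plan's own figure.** The documents give no power or item-missing rate for any self-rated scale. The only sample size is for MADRS (SAP 3). A two-sample t-test with effect size 0.45, one-sided alpha 0.10 and power 90% gives 66 per arm, so 132 completers, as stated. Then 132/0.80 = 165, against 164 stated. The 132 is used below as a reference count.

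**Inputs from the documents.** Items per form: 14, 9, 7 and 4. SHAPS forms needed: 2, so 2 x 14 = 28 answers.

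**Assumptions.** The per-item blank rate q is taken as 0.1% to 1%, with blanks independent between items.

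**SHAPS, participants who returned both forms**

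- Loss under the SAP rule: L = 1 - (1 - q)^28.
- Chance that one form has two or more blanks: p2 = 1 - (1 - q)^14 - 14q(1 - q)^13.
- Loss under a one-item rule: L1 = 1 - (1 - p2)^2.
- Interval widening, same residual SD: 1/sqrt(1 - L) - 1. At q = 1%: 1/sqrt(0.755) - 1 = 15%.

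| q | Lost, SAP rule | Interval wider by | Kept of 132 | Lost, one-item rule | Kept of 132 |
|---|---|---|---|---|---|
| 0.1% | 2.8% | 1.4% | 128 | 0.02% | 132 |
| 0.25% | 6.8% | 3.6% | 123 | 0.1% | 132 |
| 0.5% | 13.1% | 7.3% | 115 | 0.4% | 131 |
| 1% | 24.5% | 15% | 100 | 1.7% | 130 |

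If the SHAPS effect size were also 0.45 (a further assumption), power with 132 participants would be 0.90. It would fall to about 0.87 at q = 0.5% and 0.83 at q = 1%. With the one-item rule it stays at about 0.90.

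**Other scales, loss through the Day 1 form alone**, 1 - (1 - q)^k, for q from 0.1% to 1%:

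- PHQ-9 (k = 9): 0.9% to 8.6%
- GAD-7 (k = 7): 0.7% to 6.8%
- PROMIS (k = 4): 0.4% to 3.9%

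A blank on a later form of these three scales costs only that visit in the MMRM.

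**If blanks cluster within a form.** Replace the binomial with a beta-binomial with within-form correlation 0.2 (also an assumption), so a + b = 1/0.2 - 1 = 4 and a = 4q. For SHAPS:

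| q | Lost, SAP rule | Lost, one-item rule |
|---|---|---|
| 0.5% | 6.2% | 3.1% |
| 1% | 12.1% | 6.2% |

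About half of the affected forms then have exactly one blank, so the one-item rule recovers about half of the loss rather than nearly all of it.

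**The case against.** The strongest reply is that this is a choice and not an error. The rule is explicit, prespecified and the same in both arms, and giving more protection to the primary endpoint is defensible. The study is a proof of concept, powered only for MADRS. This stands as far as it goes: there is no contradiction or ambiguity in 5.1.3. But the documents give no reason for the stricter treatment of these scales.

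The size is assumed throughout. This stands. No passage gives an item-missing rate, nothing favours the upper end of the range, and independence overstates both the loss and the benefit of the fix if blanks cluster.

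A reader might infer from Protocol 4.1 ("For self-rating instruments completed at home on paper") that blanks are especially likely on the forms that matter here. The Schedule of Activities does not support that. Every SHAPS form, every GAD-7 form and the Day 1 PHQ-9 and PROMIS forms fall on clinic days. Only PHQ-9 and PROMIS on Days 22 and 36 do not, and a blank there costs one visit. Protocol 10.3.7 and 10.3.8 also provide for completeness review and queries, although under 10.3.9 staff may not override participants' answers.

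Nor are the answers on an incomplete form lost altogether, since the SAP tabulates individual items for all four scales. The rule does not reach every self-rated instrument either: the SAWB has no total and is only described.

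Finally, whether pro-rating suits each instrument depends on scoring guidance that is not in the documents. That also stands.

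**Conclusion.** The asymmetry is certain and the consequence for the models follows from the SAP's rules. The size is not known. For SHAPS it runs from 2.8% lost and an interval 1.4% wider to 24.5% lost and an interval 15% wider, given independent blanks at 0.1% to 1% per item, and it is lower if blanks cluster.

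A reader might conclude that a quarter of the SHAPS data will be lost, or that the results will be biased. The documents support neither. The first is only the top of an assumed range, and nothing in the rule treats the arms differently. The primary MADRS analysis is untouched. This is an avoidable loss of precision on secondary endpoints, of minor severity, and worth correcting because the correction is so cheap.

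**What to change.** Before database lock, extend the one-item rule in SAP 5.1.3 to SHAPS, PHQ-9 and GAD-7:

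- Exactly one item missing: total = sum of answered items x (number of items / number answered), so factors of 14/13, 9/8 and 7/6.
- Two or more items missing: total missing, as now.
- PROMIS: leave as planned. One blank is a quarter of that form.

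The cost is one SAP sentence and a line of programming, plus a check against each instrument's scoring guidance. The downside is that the missing item is taken to equal the mean of the answered items, which the SAP already accepts for the MADRS. If blanks prove rare, the change alters almost nothing.
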